10.4. Sponsor Obligations

10.4.1. Monitoring

The Sponsor monitor or designee will contact and visit the Investigator regularly and will be allowed, on request, to inspect the various records of the trial. The monitor will visit as soon as possible following enrollment of the first subject and at regular intervals during the study as deemed necessary. It will be the monitor's responsibility to inspect the source documents at regular intervals throughout the study, to verify the adherence to the protocol and the completeness, correctness and accuracy of all eCRF entries. The study monitor will have access to laboratory test reports and any other source records and data needed to verify the entries on the eCRFs, unless restricted by local laws. The Investigator agrees to cooperate with the study monitor to ensure that any problems detected in the course of these monitoring visits are resolved.

10.4.2. Regulatory Requirements

This study will be conducted in accordance with specific provisions of the associated IRB/IECs, and in accordance with the ethical principles that have their origin in the Declaration of Helsinki, and that are consistent with Good Clinical Practice (GCP) and the applicable national and regional regulatory

10.4.3. Liability and Insurance Conditions

In case of any damage or injury occurring to a subject in association with the trial medication or participation in the study, ETHICON has insurance coverage. A copy of this policy is on file at ETHICON.

11. INVESTIGATOR OBLIGATIONS

This study will be conducted in accordance with, with specific provisions of the associated IRB/IECs, and in accordance with the ethical principles that have their origin in the Declaration of Helsinki, and that are consistent with Good Clinical Practice (GCP) and the applicable national and regional regulatory.

11.1. Financial Disclosure

The investigator is responsible for updating the Sponsor if there are any changes that would affect their Financial Disclosure during the conduct of the study.

11.2. Audit and Inspection

The Investigator will make source data and documents for this study available to an appropriately qualified quality assurance auditor mandated by ETHICON, or to regulatory authority inspectors, after appropriate notification.

11.3. Confidentiality of Subject Records

The Investigator will ensure that the subjects' anonymity will be maintained. On eCRFs or other study documents submitted to ETHICON, subjects will not be identified by their names, but by an identification code *that may consist of a combination of the site, and enrollment number*. Documents not for submission to ETHICON i.e. the Subject Identification Log and original subjects' consent forms will be maintained in the Investigator Site File.

11.4. Record Retention

The Investigator will maintain all source documents that support the data collected from each subject, and all trial documents as specified by applicable regulatory requirement(s). The Investigator will take measures to prevent accidental or premature destruction of these documents. Essential documents must be retained until at least 2 years after the last approval of a marketing application worldwide, or until at least 2 years have elapsed since the formal discontinuation of clinical development of the investigational product. These documents will be retained for a longer period if required by the applicable regulatory requirements or by an agreement with ETHICON. It is the responsibility of ETHICON to inform the Investigator as to when these documents no longer need to be retained. If the responsible Investigator retires, relocates, or for other reasons withdraws from the responsibility of keeping the study records, custody must be transferred to a person who will accept the responsibility. ETHICON must be notified in writing of the name and address of the new custodian.

12. CHANGES TO THE PROTOCOL

12.1. Protocol Amendments

All protocol amendments are required to be submitted for information / consideration to the regulatory authorities, IRBs and ECs. Documentation of approval is required before implementation of amendments.

12.2. Clinical Trial Termination

Both the Investigator and ETHICON reserve the right to terminate the study at any time. Should this be necessary, the procedures will be arranged on an individual study basis after review and consultation with both parties. In terminating the study, Sponsor and the Investigator will ensure that adequate consideration is given to the protection of the subjects' interests and safety.

12.3. Use of Information and Publication

All information concerning study data, ETHICON's operations, patent application, formulas, manufacturing processes, basic scientific data, and formulation information, supplied by the Sponsor or Sponsor designee to the investigator and not previously published, is considered confidential and remains the sole property of ETHICON. The Investigator agrees to use this information only to accomplish this study and will not use it for other purposes without the sponsor's written consent.

The Investigator understands that the information developed in the clinical study will be used by ETHICON in connection with the continued development of the EVARREST product, and thus may be disclosed as required to other clinical investigators or government regulatory agencies. To permit the information derived from the clinical studies to be used, the Investigator is obligated to provide the sponsor with all data obtained in the study.

Any publication or other public presentation of results from this study requires prior review by ETHICON. Draft abstracts, manuscripts, and materials for presentation at scientific meetings must be sent to the sponsor at least 30 working days prior to abstract or other relevant submission deadlines. Authorship of publications resulting from this study will be based on generally accepted criteria for major medical journals.

The investigator understands not to use the name of Johnson & Johnson (J&J), Ethicon, ETHICON™ Biosurgery, Fibrin Pad (EVARREST®), EVARREST® Fibrin Sealant Patch, EVARREST® Sealant Matrix or any its employees, in any publicity, news release or other public announcement, written or oral, whether to the public, press or otherwise, relating to this protocol, to any amendment hereto, or to the performance hereunder, without the prior consent of ETHICON.

Appendix 1: U.S. Center for Disease Control (CDC) Guideline for Prevention of SSI Surgical Wound

Classification

CLASS I/CLEAN:

An uninfected operative wound in which no inflammation is encountered and the respiratory, alimentary, genital and urinary tracts are not entered. Clean wounds are primarily closed and, if necessary, drained with closed drainage. Operative incisional wounds that follow non-penetrating (blunt) trauma should be included in this category if they meet these criteria.

CLASS II/CLEAN-CONTAMINATED:

An operative wound in which the respiratory, alimentary, genital and urinary tract is entered under controlled conditions and without unusual contamination. Specifically, operations involving the biliary tract, appendix, vagina, and oropharynx are included in this category, provided no evidence of infection or major break in technique is encountered.

CLASS III/CONTAMINATED:

Open, fresh, accidental wounds, operations with major breaks in sterile technique or gross spillage from the gastrointestinal tract, and incisions in which acute, nonpurulent inflammation is encountered.

CLASS IV/DIRTY OR INFECTED:

Old traumatic wounds with retained devitalized tissue and those that involve existing clinical infection or perforated viscera. This definition suggests that the organisms causing postoperative infection were present in the operative field before the operation.

	8.3 Demographic and Baseline Characteristics	9
	8.4 Primary and Secondary Endpoint Analyses	9
	8.4.1 Primary Endpoint Analyses.....	9
	8.4.2 Secondary Endpoint Analyses.....	9
	8.4.3 Safety Analyses	10
	8.5 Plans for Interim Analysis	10
	8.6 Handling of Missing Data.....	10
	8.7 Subgroup Analysis	10

1 Study Design

The objective of this study is to evaluate the safety and hemostatic effectiveness of EVARREST Fibrin Sealant Patch (EVARREST) in controlling mild or moderate soft tissue and parenchymal bleeding during open hepatic, abdominal, pelvic, retroperitoneal, and thoracic (non-cardiac) surgery in pediatric patients.

This is an open-label, multicenter, single-arm study evaluating the safety and effectiveness of EVARREST in controlling mild or moderate bleeding in hepatic parenchyma or soft tissue for which standard methods of achieving hemostasis are ineffective or impractical during surgery in pediatric patients.

For this study, approximately 12 sites in US and UK will be utilized for consecutive screening and enrollment. Subjects will be considered as enrolled when the Informed Consent and Assent Form(s), as appropriate, is signed. Eligible subjects will be treated with EVARREST. Subjects will be followed post-operatively through hospital discharge and at 30 days (± 14 days) post-surgery.

At least thirty-five (35) pediatric subjects with an appropriate mild or moderate bleeding TBS will be enrolled in this study. The age of the subjects enrolled in the study will be from 1 month to <18 years. This will include a minimum of 4 subjects aged 1 month (≥ 28 days from birth) to <1 year.

The Target Bleeding Site (TBS) will be the only region evaluated for the primary endpoint and all secondary effectiveness endpoints. The TBS is defined as the first actively bleeding site identified during the soft tissue or hepatic dissection related to the primary operative procedure with challenging mild to moderate bleeding. This site will then be assessed for hemostatic effectiveness after product application as described below.

Once the TBS is identified, the surgeon will immediately apply EVARREST at the actively bleeding TBS. The size of the treatment article applied should be sufficient for coverage of the entire TBS and should overlap the bleeding source with a margin of 0.5-1 inch (1-2 cm).

After placement of EVARREST, the surgeon will apply firm continual manual compression over the entire bleeding area until 4 minutes from TBS identification. The surgeon may use a surgical sponge (laparotomy pad or surgical gauze) to assist in providing adequate pressure over the entire surface area.

Hemostasis is defined as no detectable bleeding at the TBS. Absolute time to hemostasis, defined as the absolute time elapsed from TBS identification to the last moment in time at which detectable bleeding at the TBS is observed, will be recorded.

Hemostasis will be assessed at 4 minutes from TBS identification by carefully releasing manual compression and removing the surgical sponge (if used). Hemostasis will also be assessed at 10 minutes from TBS identification and at initiation of final fascial closure. The absolute time to hemostasis will be recorded. EVARREST should not be removed after bleeding has been stopped.

If bleeding requiring treatment occurs after the 4 minute assessment, the surgeon can retreat the TBS with EVARREST or revert to their standard of care.

Hemostasis will be assessed at 4 minutes and 10 minutes after TBS identification and absolute time to hemostasis is recorded regardless of any additional treatments.

EVARREST can only be used on a single TBS to be evaluated. If additional soft tissue or hepatic parenchymal bleeding sites are identified, the surgeon should treat according to their standard of care.

Primary Endpoint:

The primary endpoint in this study will be the absolute time to hemostasis defined as the absolute time elapsed from TBS identification to the last moment in time at which detectable bleeding at the TBS is observed.

Secondary Endpoints:

- Proportion of subjects achieving hemostatic success at 4 minutes following TBS identification and no bleeding requiring treatment at the TBS any time prior to final fascial closure
- Proportion of subjects achieving hemostatic success at 10 minutes following TBS identification and no bleeding requiring treatment at the TBS any time prior to final fascial closure
- Proportion of subjects with no re-bleeding at the TBS

Safety Endpoints:

- Incidence of adverse events that are potentially related to bleeding at the TBS
- Incidence of adverse events that are potentially related to thrombotic events
- Incidence of re-treatment at the TBS
- Incidence of any adverse events, which will be collected from time of TBS identification, throughout the follow-up period
- Laboratory tests (including hemoglobin, hematocrit, platelets)
- Estimated intra-operative blood loss

- Number and volume of blood products transfused

2 Treatment Assignment

This is a single-arm study in which all subjects will have EVARREST applied at the actively bleeding TBS during the surgical procedure.

3 Randomization and Blinding Procedures

As this is a single-arm study, no randomization will occur, and no blinding procedures are required.

4 Interval Windows

Interval windows for the purpose of analysis in this study will not be defined outside of those for visit scheduling. The final visit occurs approximately 30 days after surgery. There will be a window of 14 days around the scheduling of the 30-day follow-up visit, and any information entered in the eCRFs at this visit will correspond to the associated visit. There will be no assigning of observations to time points outside of the visit to which they are recorded in the eCRFs.

5 Primary and Secondary Endpoints and Associated Hypotheses

Study endpoints are presented under the Study Design section. No hypotheses testing will be performed for this study.

6 Levels of Significance

No formal hypothesis testing will be performed for this study. A two-sided 95% distribution-free confidence interval (CI) for median absolute time to hemostasis will be estimated. In addition, for success/failure secondary endpoints (4 and 10 minutes hemostasis endpoints), two-sided 95% CIs will be estimated for the proportion of successes in EVARREST treated subjects, using the Clopper-Pearson method. All CIs will be estimated for descriptive purposes only.

7 Analysis Sets

The following four analysis sets are defined:

- All Enrolled Set (AES) consists of all subjects who provided informed consent or assent form for this study.
- Full analysis set (FAS or intent-to-treat set) consists of all enrolled and eligible subjects for whom TBS was identified. Subjects who do not complete the procedure after TBS identification will be included in the FAS analysis.
- Evaluable analysis set (or per-protocol [PP] set) consists of all FAS subjects who have no major protocol deviations affecting the primary endpoint and have data available for this endpoint.
- Safety analysis set will consist of all subjects who received treatment.

The primary endpoint analysis will be based on the FAS. An analysis based on the Evaluable set will also be performed for this endpoint, however, it will be considered supportive. Major protocol deviations will be determined prior to database lock.

In addition, for both FAS and Evaluable set, the absolute time to hemostasis will be analyzed descriptively separately for subjects who achieved hemostasis with and without additional treatments being required.

All secondary endpoints will be analyzed using the FAS, while safety endpoints will be analyzed using the Safety analysis set.

8 Sample Size Justification

No formal sample size calculation was performed for this study as no formal statistical hypotheses are being tested. However, a total of 35 subjects with an identified TBS are considered adequate to provide sufficient information to evaluate data descriptively.

9 Analyses to be Conducted

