4.2. Inclusion Criteria

Pre-operative:

1. Pediatric subjects aged ≥ 28 days (≥ 1 month) to < 18 years, requiring non-emergent open hepatic, abdominal, retroperitoneal, pelvic or thoracic (non-cardiac) surgical procedures;
 - i) A minimum of 4 subjects to be enrolled will be aged ≥ 28 days to < 1 year.
2. The subject's parent/legal guardian must be willing to give permission for the subject to participate in the trial and provide written Informed Consent for the subject. In addition, assent must be obtained from pediatric subjects who possess the intellectual and emotional ability to comprehend the concepts involved in the trial. If the pediatric subject is not able to provide assent (due to age, maturity and/or inability to intellectually and/or emotionally comprehend the trial), the parent/legal guardian's written Informed Consent for the subject will be acceptable for the subject to be included in the study.

Intra-operative

3. Presence of an appropriate mild or moderate bleeding soft tissue or hepatic parenchyma Target Bleeding Site (TBS) identified intra-operatively by the surgeon;
4. Ability to firmly press trial treatment at TBS until 4 minutes after TBS identification.

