4.3. Exclusion Criteria

Pre-operative

1. Subjects with known intolerance to blood products or to one of the components of the study product or is unwilling to receive blood products;
2. Female subjects, of childbearing age (i.e. adolescent), who are pregnant or nursing;
3. Subject is currently participating or plan to participate in any other investigational device or drug study without prior approval from the Sponsor;
4. Subjects who are known, current alcohol and/or drug abusers
5. Subjects admitted for trauma surgery
6. Subjects with any pre or intra-operative findings identified by the surgeon that may preclude conduct of the study procedure.
7. Subjects that have received a COVID-19 vaccine either 4 weeks prior to surgery or scheduled to receive COVID-19 vaccine within the 30-day follow-up period.

Intra-operative

8. Subject with TBS in an actively infected field (Class III Contaminated or Class IV Dirty or Infected) ¹
9. TBS is from large defects in arteries or veins where the injured vascular wall requires repair with maintenance of vessel patency and which would result in persistent exposure of EVARREST to blood flow and pressure during healing and absorption of the product;

¹ Appendix 1
BIOS-16-001 EVARREST MM Amendment 6, 02 November 2023
EudraCT Number: 2019-004657-89

10. TBS with major arterial bleeding requiring suture or mechanical ligation;

11. Bleeding site is in, around, or in proximity to foramina in bone, or areas of bony confine.

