8.2.1. Analysis Sets

The following four analysis sets defined:

- All Enrolled Set (AES) consists of all subjects who provided informed consent or assent form for this study.
- Full analysis set (FAS or intent-to treat) consists of all enrolled and eligible subjects for whom TBS was identified. Subjects who do not complete the procedure after TBS identification will be included in the FAS analysis.
- Evaluable analysis set (or per protocol) consists of all FAS subjects who have no major protocol deviations affecting the primary effectiveness endpoint and have data available for this endpoint.
- Safety analysis set will consist of all subjects who received treatment.

The primary endpoint analysis will be based on the Full analysis set. The evaluable analysis will be considered supportive.

Major protocol deviations will be determined prior to database lock.

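### The full analysis set depends on eligibility with no time point fixed for judging it, so a treated subject re-judged ineligible after T0 could drop out of every effectiveness analysis

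*SAP*

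**What the plan says.** SAP 7 and protocol 8.2.1 define the FAS in the same terms: it "consists of all enrolled and eligible subjects for whom TBS was identified". The next sentence adds: "Subjects who do not complete the procedure after TBS identification will be included in the FAS analysis". The Evaluable set is the part of the FAS without major deviations affecting the primary endpoint and with data for it. The Safety set carries no eligibility condition: "Safety analysis set will consist of all subjects who received treatment".

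SAP 7 assigns the effectiveness endpoints as follows: "The primary endpoint analysis will be based on the FAS" and "All secondary endpoints will be analyzed using the FAS". SAP 9.6 counts missing secondary outcomes as failures.

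Protocol 7.1.3 has intra-operative eligibility confirmed before the stopwatch is started and the patch applied. The intra-operative criteria in protocol 4.2 and 4.3 include inclusion 4, "Ability to firmly press trial treatment at TBS until 4 minutes after TBS identification", and exclusion 10, "TBS with major arterial bleeding requiring suture or mechanical ligation". Exclusion 6, listed among the pre-operative criteria, also reaches into the operation: "Subjects with any pre or intra-operative findings identified by the surgeon that may preclude conduct of the study procedure". Protocol 7.1.3 further requires that manual compression be able to control all bleeding at the site.

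**The concern.** The word eligible in the FAS definition has no date attached. Protocol 7.1.3 governs when the surgeon checks eligibility, but the FAS definition does not refer to that check, and nothing bars a later re-judgement.

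Some criteria overlap with what a failed application reveals:

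- **Exclusion 10.** If bleeding continues, the re-treatment instructions in protocol 7.1.3 have the patch removed, the site inspected and the need for other primary measures considered. That is close to the judgement in exclusion 10, and it is prompted by failure.
- **Control by compression.** Bleeding that persists under pressure is a treatment failure and also evidence against this site requirement.
- **Exclusion 6.** It is an open surgeon judgement with no stated cut-off.
- **Screen failure.** The instruction to document intra-operative screen failures sits among the surgical activities without a stated end point.

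The trial is open label, and the surgeon who identifies the site also sees the result. A treated failure called ineligible would leave both the FAS and the Evaluable set. The rule that missing counts as failure could not bring the subject back, because it applies only within the FAS.

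**Working it through.** **1. Check of the interval method.** The Clopper-Pearson limits for x successes in n are the 0.025 quantile of Beta(x, n−x+1) and the 0.975 quantile of Beta(x+1, n−x). Applied to the earlier pediatric study in protocol 1, they reproduce all four stated intervals: 16/20 gives 56.3–94.3%, 12/20 gives 36.1–80.9%, 19/20 gives 75.1–99.9% and 18/20 gives 68.3–98.8%.

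**2. Inputs for the illustration.** N = 35 comes from protocol 8.1 and SAP 8. The success counts are assumptions. For 4 minutes, the earlier study's 80% gives 0.80 × 35 = 28, with 31 as a more favourable case. For 10 minutes, its 95% gives 0.95 × 35 = 33.25, taken as 33. The number of failures removed, k, is also an assumption.

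**3. Effect on the 4-minute proportion.** Removing k failures changes x/35 to x/(35−k). Going from n to n−1 adds x/[n(n−1)].

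| Assumed result | k | Estimate | 95% CI |
|---|---|---|---|
| 28/35 | 0 | 80.0% | 63.1–91.6 |
| 28/34 | 1 | 82.4% | 65.5–93.2 |
| 28/33 | 2 | 84.8% | 68.1–94.9 |
| 28/32 | 3 | 87.5% | 71.0–96.5 |
| 28/31 | 4 | 90.3% | 74.2–98.0 |

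The first step is 28/(35×34) = 2.4 points and the fourth is 28/(32×31) = 2.8 points. The lower limit rises by 2.4 points at the first step (65.5 − 63.1) and by 3.2 at the fourth (74.2 − 71.0).

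In the more favourable case, 31/35 is 88.6% (73.3–96.8). Removing all four failures gives 31/31 = 100% (88.8–100).

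**4. Effect on the 10-minute proportion.** 33/35 is 94.3% (80.8–99.3). Removing one failure gives 33/34 = 97.1% (84.7–99.9), and removing both gives 33/33 = 100% (89.4–100).

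**5. Effect on the primary median.** At n = 35 the median is the 18th ordered time. The distribution-free interval runs from the 12th to the 24th ordered time, with coverage 95.9% from Binomial(35, 0.5). The upper limit exceeds 4 minutes only if at least 35 − 24 + 1 = 12 times do, and the median only if at least 35 − 18 + 1 = 18 do. With seven times above 4 minutes, neither exceeds 4 minutes.

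With three of those seven removed, n = 32 and the interval runs from the 10th to the 23rd ordered time. Its upper limit would exceed 4 minutes only with 32 − 23 + 1 = 10 late times, and four remain. The mean and maximum, which SAP 9.1 also reports, would fall if late times were removed. The documents give no basis for sizing that.

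**The case against.** The strongest defence is the order of events in protocol 7.1.3: if it is followed, T0 cannot start until eligibility is confirmed, so a FAS defined by T0 would largely coincide with the present one. Several provisions support this reading. Inclusion 4 is worded as an ability, which can be judged from the site beforehand; failure to hold pressure is then naturally a deviation for the Evaluable set. Exclusion 6 looks forward to findings that would prevent the procedure. The FAS expressly keeps non-completers. The synopsis counts additional treatment after the 4-minute endpoint as failure of that endpoint. Protocol 10.3.2 names treated subjects and screening failures separately. No text tells anyone to reclassify a treated failure.

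Most of this stands, and it limits the point. A reader might infer that some criteria can be judged only once the patch is on; the pre-T0 check and the wording of inclusion 4 do not support that. A reader might also infer that a subject whose compression was not completed would be lost; the sentence on non-completers answers that.

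What remains is that the defence rests on the conduct section, to which the FAS definition does not refer. Keeping non-completers does not settle the status of a subject later called ineligible.

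It is also fair to say that SAP 6 makes all intervals descriptive, so no error rate is affected. However, the protocol synopsis says the lower limits will be used for inference, and those limits move. A descriptive estimate can also mislead if failures are removed selectively.

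**Conclusion.** The point holds as a gap in the definition, and it should be closed. As written, both documents allow a treated subject whose violation is found or re-judged at or after T0 to leave every effectiveness analysis and remain only in the Safety set. The documents do not show that this will happen or how often.

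A reader might conclude that every effectiveness estimate is biased upward. The documents do not support that. The primary endpoint is a time, so a favourable bias would be downward, and its median and interval barely respond at this sample size. The exposure is mainly in the 4- and 10-minute proportions: about 2.4 to 2.8 points per failure removed at 4 minutes, assuming 28 of 35 succeed and up to four failures are removed. Both the success count and the number removed are assumptions.

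**What to change.** In protocol 8.2.1 and SAP 7, define the FAS as all consented subjects with an identified TBS for whom the stopwatch (T0) was started, regardless of any eligibility violation found at or after T0. Handle such violations only in the Evaluable set, and list each subject concerned with the reason and whether the violation was identified before or after the 4-minute assessment. Because T0 precedes application, every treated subject is then in the FAS.

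The cost is about one sentence in each document, with the protocol change following the amendment route in protocol 12.1. Treatment and assessments do not change. The downside is that a few ineligible subjects may stay in the primary analysis and slightly lower the success rate; the Evaluable analysis of the primary endpoint would show that endpoint without them.
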